**INVESTIGATION OF THE RELATIONSHIP OF MUSCULAR ENDURANCE WITH
PAIN, NECK AWARENESS, AND KINESIOPHOBIA IN PATIENTS WITH
CERVICAL DISC HERNIATION**

Hacettepe University Non-Interventional Clinical Researches Ethics Committee

(#GO 2019 / 16-14, Date: 18.06.2019).

MATERIALS AND METHODS

Participants

This study was carried out with patients diagnosed with cervical disc herniation who were presented on an outpatient basis to Hacettepe University, Faculty of Physical Medicine and Rehabilitation between July 2019 and July 2020. Patients with cervical disc herniation who met the inclusion criteria were given detailed information about the study, and signed a consent form containing the content, purpose, and evaluation methods of the study. The study was approved by the Hacettepe University Non-Interventional Clinical Researches Ethics Committee (#GO 2019 / 16-14, Date: 18.06.2019).

The study included 36 patients who met the inclusion criteria: being 18-65 years old, having a diagnosis of cervical disc herniation confirmed by MR radiography, direct radiography, and clinical and physical examination, having neck pain at rest for 3 months or more with a severity of 2 or above according to the Visual Analogue Scale (VAS) (18), having a score of 5 or more from the NDI (19), and being able to comply with the instructions of the physiotherapist. The NDI was developed to evaluate the disability caused by chronic neck pain. It was developed as the neck version of the Oswestry Low Back Pain Disability Questionnaire, which was developed by Vernon et al. Each question is scored between 0 and 5 and the level of disability of the patients is classified according to the following score scheme: 0-4 points, no disability; 5-14 points, mild disability; 14-24 points, moderate disability; 25-34 points, severe disability; and, 35-50 points, complete disability (19, 20).

Patients with spinal tumors/deformities/congenital malformations and who underwent cervical or upper extremity surgery in the previous 6 months were excluded from the study.

In a post-hoc power analysis for the sample size of the study, taking into account the correlation between neck pain during activity and cervical deep flexor muscle endurance of individuals, the statistical significance of Alpha was 5% and the confidence interval was 95%, the strength of the study ($1-\beta$) was 86% with 36 individuals with cervical disc herniation.

Assessments

Following evaluations were performed after the age, height (cm), weight (kg), body mass index (kg/m^2), gender, diagnosis, treatments received, and exercise habits of the patients were recorded;

Assessment of Muscular Endurance

The **endurance of the neck flexor muscles** was evaluated by placing the head on a 6 cm elevation in the supine hook position. With the removal of the head support, the maximum time that the patient could maintain this position without disturbing was recorded in seconds. The test was terminated after a 5-degree deviation occurred in the goniometer which followed the vertical angle of the mandible (21).

Neck extensor muscle endurance was evaluated with the arms on the side of the body in the prone position. The head and neck of the patients were positioned so that they hang from the bed, starting from chest level; and 2 kg of sand weight was placed behind the head corresponding to the C6 level with the help of a 10 cm Velcro. The maximum amount of time the patient could hold his head in this position was recorded in seconds (14).

Cervical deep flexor muscle endurance was evaluated in the supine hook position. The patients were asked to put their hands on their abdomen and look at chest level by pulling their chin inward. The maximum time in seconds they could hold their head in this position by raising their head approximately 2.5 cm was noted (22).

In order to evaluate the **trunk flexor muscle endurance**, the patients were asked to clamp their hands on the opposite shoulders in the supine hook position. They were asked to lift up the upper body until the lower end of the scapula lifted off the ground, and the maximum time in seconds they could maintain this position was recorded (14).

In order to evaluate the **endurance of the trunk extensor muscles**, the patients were placed in the prone position with the upper body hanging from the bed. The point where the bed touches the body of the individual was set to be *spina iliaca anterior superior*. The lower limb was fixed on the bed by the evaluator. In order not to lose the balance, the participants were asked to get support with their hands first, and when they were ready, they were asked to bring both hands together on their neck and lift their body parallel to the ground. The maximum time in which they could hold this position was noted in seconds (23).

In order to evaluate the **endurance of the trunk lateral flexor muscles**, the patients were placed in a side-lying position and were asked to pull their knees gently on their abdomen. The upper leg of the patient was placed in front of the other foot. The body weight of the patient was positioned on the forearm and feet, and the upper hand was placed on the opposite shoulder.

They were asked to elevate the hip until the pelvis and trunk reached a horizontal position. In the meantime, the individual was warned not to get support from the upper leg. After the movement was taught, measurements were made for the right and left sides separately, and the maximum time that they could maintain the position was recorded for both sides in seconds (23).

The endurance of the trunk stabilizer muscles was evaluated with the bridge test in prone. The individual was initially asked to place in the prone position supported on the knee and forearms. Then, they were asked to stand on their forearms and toes by raising their knees, and then they were asked to maintain this position. The time they held the position was noted in seconds (24).

Upper extremity muscle endurance was evaluated in a modified push-ups exercise position. In the prone position, hands were placed shoulder-width apart on the ground, and the trunk was asked to be brought closer to the ground with elbow flexion. Care was taken to ensure that the body weight was only on the knees and hands. After the movement was taught, the number of repetitions the patient could do over 30 seconds was noted (25).

M. serratus anterior and m. trapezius muscles' endurance were evaluated via the scapular muscle endurance test. For the test, the patient was in standing position with shoulder and elbow flexion angles at 90°. A dynamometer (Feta 0202 1kg/10N) with a resistance of 1kg/10N was placed between hands by placing a 30 cm ruler between the elbows. The patients were asked to take the dynamometer in the position that they would be most comfortable to hold, bring their shoulders to external rotation, and pull it with both hands. The time in which they were able to hold the position without dropping the ruler was noted in seconds (14).

All muscular endurance evaluations of the patients are shown in Figure 1.

Assessment of Level of Pain

In order to evaluate the pain levels of the patients, a 10-cm Visual Analogue Scale (VAS), which was developed by Price et al. to evaluate the pain level in patients with chronic pain, was used (18). In the VAS, there is a value of 0 at the beginning of the 10 cm line and 10 at the end. It was stated to the patients that the value 0 means no pain, and the value 10 means the most severe pain. Then, they were asked to rate their neck pain on the 10 cm horizontal line. The

marked point was measured with a ruler and noted in cm. Resting pain, pain during activity, and pain at night were questioned, separately.

Assessment of Neck Awareness

In order to evaluate the neck awareness levels of the patients, the Fremantle Neck Awareness Questionnaire (FreNAQ) which developed by Wand et al. to assess neck awareness in patients with chronic neck pain, was used. The FreNAQ consists of 9 items about neck pain, attention, and proprioceptive awareness. Each question is scored between 0 and 4 (0 = Never / I never feel this way, 1 = I rarely feel this way, 2 = I sometimes feel this way, 3 = I often feel this way, 4 = I often or always feel this way). The total score of the questionnaire is between 0 and 36. Higher scores indicate higher neck awareness. The Turkish version of this questionnaire, whose adaptation was conducted by Onan et al., was used in this study (26, 27).

Assessment of the Fear of Movement

The fear of movement was assessed by the Tampa Kinesiophobia Questionnaire developed by Kori et al. The questionnaire evaluating injury avoidance and fear of movement consists of 17 items, and each item is scored between 1 and 4 (1 = Strongly disagree, 4 = Strongly agree). The total score ranges from 17 to 68. Higher scores indicate a higher kinesiophobia level (28). The Turkish version of the questionnaire, which was adapted to Turkish by Yılmaz et al., was used in current study (29).

Statistical analysis

Windows based SPSS 22 (Statistics Program for Social Sciences, version 22) (<http://www.spss.com.tr>) analysis program was used for all statistical analyses. Qualitative data are shown with number (n) and percentage (%) in the expression of the descriptive analysis results of the data. Mean (X), minimum and maximum values, and standard deviation (SD) were used for quantitative variables. The conformity of the variables to normal distribution was tested with Histogram Analysis, coefficient of variation, skewness-kurtosis, Kolmogorov-Smirnov Test, and "Normal Q-Q Plot" and "Detrended Normal Q-Q Plot". Since it was determined that the data did not conform to the normal distribution, it was decided that non-parametric conditions were met. Evaluations of the relationships between muscular endurance and pain, neck awareness, and fear of movement in participants with cervical disc herniation were made on the basis of the Spearman's correlation coefficient (rho). The strength of the relationships was assumed: $r > 0.90$ very strong; 0.70-0.90 strong; 0.40-0.70 moderate; 0.20-

0.40 weak, and $r < 0.20$ very weak/insignificant correlation. The statistical significance level (p) was accepted as 0.05 (30).

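### The 86% power is a post-hoc figure for one pair of measures but is labelled as the power of the study; for weak correlations and the lower edge of moderate ones, power with 36 patients is well below that

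*Protocol*

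**What the plan says.** The power statement is one sentence in the Participants section. It begins "In a post-hoc power analysis for the sample size of the study, taking into account the correlation between neck pain during activity" and names cervical deep flexor endurance as the other variable. It continues "the statistical significance of Alpha was 5% and the confidence interval was 95%, the strength of the study", and the figure that follows "was 86% with 36 individuals with cervical disc herniation". It gives neither the size of the correlation nor whether the test was one- or two-sided. No other power figure appears.

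The planned analysis is wider than that pair. Under Statistical analysis, "Evaluations of the relationships between muscular endurance and pain, neck awareness, and fear of movement in participants with cervical disc herniation" are to be made with Spearman's rho at a significance level of 0.05. The Assessments section lists nine endurance tests. For the trunk lateral flexors "measurements were made for the right and left sides separately", which makes ten endurance values. The outcomes are three pain ratings ("Resting pain, pain during activity, and pain at night were questioned, separately"), the neck awareness score and the kinesiophobia score.

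The protocol also grades correlations by size: "0.70-0.90 strong; 0.40-0.70 moderate", with 0.20 to 0.40 called weak.

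**The concern.** Power belongs to a particular test at a particular true effect. The protocol computes it for one pair, after the data were in, and then attaches it to the whole study as support for its sample size. Without the coefficient, a reader cannot check the 86% or turn it into a correlation that the study could detect.

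What is at stake is how non-significant results are read. Someone who takes 86% as study-wide could treat a non-significant correlation with, say, night pain or kinesiophobia as good evidence of no relationship. For correlations that the protocol itself calls weak, a non-significant result is an ordinary outcome with 36 patients even when the relationship is real.

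**Working it through.** **Inputs.** From the protocol: n = 36, alpha = 0.05, stated power 86%, Spearman's rho, and the strength scale. Assumed, because not stated: a two-sided test (one-sided shown as a variant), no multiplicity adjustment, and bivariate normal data without ties for the simulation.

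**1. The protocol's 86%.** It cannot be recomputed, because the coefficient and sidedness are missing. It can be inverted. With Fisher's z, power ≈ Φ(atanh(ρ)·√(n−3) − z_α). Setting power to 0.86 (normal quantile 1.080) gives:

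- two-sided: atanh(ρ) = (1.960 + 1.080)/√33 = 0.529, so |ρ| = 0.485
- one-sided: atanh(ρ) = (1.645 + 1.080)/√33 = 0.474, so |ρ| = 0.442

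Other formulas move this a little:

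| Method | Two-sided | One-sided |
|---|---|---|
| Noncentral t | 0.463 | 0.421 |
| Exact bivariate normal | 0.479 | 0.435 |
| Fisher z with bias term | 0.480 | 0.437 |
| Fisher z | 0.485 | 0.442 |
| Bonett-Wright variance | 0.493 | 0.449 |
| Fisher z, variance factor 1.06 | 0.497 | 0.453 |

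So the 86% corresponds to |rho| of about 0.46 to 0.50 two-sided, or 0.42 to 0.45 one-sided. Simulating the Spearman test itself gives about 0.49 and 0.44 to 0.45.

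**2. Number of pairs.** 10 endurance values × 5 outcomes = 50, or 9 × 5 = 45 if the two lateral flexor sides are combined. Less the named pair, 49 or 44 remain. The count only shows how far the label reaches; the powers below are per test and do not depend on it.

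**3. Power per test with 36 patients.** Bivariate normal data were simulated with Pearson r = 2·sin(π·rho/6) and tested with t = rho·√(34/(1−rho²)) on 34 degrees of freedom. The two-sided critical value is 2.032/√(34 + 2.032²) = 0.329; the one-sided value is 0.279.

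| True \|rho\| | Protocol's band | Two-sided power | One-sided power |
|---|---|---|---|
| 0.20 | weak, lower edge | 21% | 31% |
| 0.30 | weak | 42% | 55% |
| 0.40 | moderate, lower edge | 67% | 78% |
| 0.46 | moderate | 81% | |
| 0.49 | moderate | 86% | |
| 0.55 | moderate | 94% | |
| 0.60 | moderate | 97% | |

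Repeat runs move the 0.30 and 0.40 entries between 42% and 43% and between 67% and 68%. The Fisher formula agrees: at 0.40, Φ(0.4236 × 5.745 − 1.960) = Φ(0.474) = 68%.

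**4. Ties.** The protocol says "Since it was determined that the data did not conform to the normal distribution, it was decided that non-parametric conditions were met", so the simulation model is only approximate. Rounding both variables to whole units gives two-sided power of 42%, 67%, 81% and 85% at 0.30, 0.40, 0.46 and 0.49. An assumed 25% of patients tied at the floor of both measures gives 40%, 64%, 78% and 84%. The picture does not change.

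**5. What a non-significant result can hide.** Take an observed rho of 0.32, tested two-sided. It is below 0.329, so not significant. With standard error √((1 + 0.32²/2)/33) = 0.178 on the z scale, the 95% interval is tanh(0.332 ± 1.96 × 0.178), or −0.02 to 0.59. It reaches well into the moderate band. This example is illustrative and needs the two-sided assumption: against the one-sided critical value of 0.279, 0.32 in the tested direction would be significant.

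**The case against.** The strongest reply is that the sentence carries its own limitation. It says the analysis is post hoc, names the pair, and gives alpha and n. Nowhere does it say that 86% holds for every pair, and quoting power for one named relationship is common. Enrolment is complete, no decision rule uses the figure, and the protocol grades correlations by size as well as by p-value, so 0.32 would be called weak rather than absent. All of that stands, and it limits the harm to one of interpretation. It does not remove the problem: this is the only power figure, it is offered in support of the sample size, and its label is the study's.

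Four stronger readings are tempting, and the document does not support them.

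- *That 86% is miscalculated.* Without the coefficient and sidedness this cannot be tested, and plausible values reproduce it.
- *That the 86% merely restates the pair's p-value.* That would follow if the observed coefficient was the input. The wording suggests this but does not say so.
- *That the study is underpowered throughout.* From a true |rho| of about 0.49 upward, two-sided power per test is at least 86%. That covers roughly the upper two-thirds of the moderate band and all of the strong band.
- *That the protocol treats non-significance as no relationship.* It says no such thing; the risk lies with the reader.

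Reporting confidence intervals may also be covered in an analysis plan that is not at hand. It is suggested here as part of the remedy, not listed as an omission.

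**Conclusion.** The point holds as one of scope and labelling. The 86% is a post-hoc figure for activity pain with cervical deep flexor endurance, and it does not give the power for the other 44 to 49 pairs. Per test, it applies only at a true |rho| near 0.46 to 0.50 if two-sided, or 0.42 to 0.45 if one-sided. Across the protocol's weak band, power runs from about 21% to 67% two-sided, or 31% to 78% one-sided, so the conclusion for weak correlations does not depend on sidedness. At the lower edge of moderate it is more sensitive: 67% against 78%.

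These figures assume unadjusted 5% tests and are approximate for tied or non-normal data. Any multiplicity adjustment would lower power further. The matter is worth correcting because it affects how null results are read. It does not undermine the data or the choice of test.

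**What to change.** Limit the 86% to the correlation of activity pain with cervical deep flexor endurance, describe it as post hoc, and give the coefficient and sidedness used; or remove it. For the study as a whole, state for example:

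> With 36 patients and two-sided alpha 0.05, per test and before any multiplicity adjustment, Spearman's test has about 80% power for |rho| of about 0.46, 67% for 0.40 and 42% for 0.30 (approximate for tied or non-normal data).

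If the tests were one-sided, say so and use about 78% for 0.40 and 55% for 0.30. Report a 95% confidence interval with each rho, so that a non-significant result is not read as no relationship.

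The cost is one rewritten sentence and one interval per coefficient, with no new patients, data or tests. The downside is a less favourable power statement.

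### Should the descriptive tables switch from mean and SD to median and quartiles because the data were judged non-normal?

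*Protocol*

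**What the plan says.** The protocol's Statistical analysis section does three things in turn. For description it says: "Mean (X), minimum and maximum values, and standard deviation (SD) were used for quantitative variables". It then lists several normality checks (histograms, coefficient of variation, skewness and kurtosis, the Kolmogorov-Smirnov test, Q-Q plots) and concludes: "Since it was determined that the data did not conform to the normal distribution, it was decided that non-parametric conditions were met". Finally it bases the relationships of endurance with pain, neck awareness and fear of movement on Spearman's rank correlation, at a significance level of 0.05.

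The variables are of several kinds. Most endurance tests are hold times; for the neck extensors, for example, "The maximum amount of time the patient could hold his head in this position was recorded in seconds". Upper extremity endurance is a count: "the number of repetitions the patient could do over 30 seconds was noted". Pain is a 0 to 10 cm line, the FreNAQ total runs from 0 to 36 and the Tampa total from 17 to 68.

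**The concern.** The normality finding changes the inferential method but not the description of the same variables. That looks inconsistent, because a common convention pairs rank methods with the median and quartiles.

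There is also a plausible mechanism for harm. A hold time cannot fall below zero and the protocol states no maximum, so a few patients with long holds could raise the mean and inflate the SD. With 36 patients, a handful of extreme values could matter. The minimum and maximum each come from a single patient and do not show where the middle half of the sample lies. A reader who treats the mean minus 2 SD as a lower limit could arrive at a negative time. What is at stake is the printed picture of the typical patient's endurance and its spread.

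**Working it through.** **The plan's own figure.** The only computed figure in the protocol is the post-hoc power of 86% with 36 patients at alpha 5%, for the correlation of activity pain with deep flexor endurance. It does not bear on the descriptive statistics. It cannot be reproduced either, since no correlation is given. Solving the Fisher z formula backwards, two-sided, r = tanh[(1.960 + 1.080) × √(1/33)] = 0.485. With the Spearman variance factor of 1.06 it is 0.497. Neither value depends on a mean, SD, median or quartile.

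**How far could the mean mislead?** The document gives no skewness, no CV and no data, so this step rests on two assumptions: log-normal hold times, and a CV between 0.3 and 1.2. Then mean/median = √(1 + CV²), and the quartiles divided by the median are exp(±0.6745 s) with s² = ln(1 + CV²).

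| CV | Mean / median | (Mean − SD) / median | Quartiles / median |
|---|---|---|---|
| 0.3 | √1.09 = 1.04 | 0.73 | 0.82 to 1.22 |
| 0.5 | √1.25 = 1.12 | 0.56 | 0.73 to 1.38 |
| 0.8 | √1.64 = 1.28 | 0.26 | 0.62 to 1.61 |
| 1.0 | √2.00 = 1.41 | 0.00 | 0.57 to 1.75 |
| 1.2 | √2.44 = 1.56 | −0.31 | 0.53 to 1.89 |

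So the gap between mean and median runs from 4% to 56%, depending entirely on an assumed CV. For a symmetric non-normal distribution it is zero. The protocol reports only a failure of normality, which fits either case.

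**Negative times.** Mean − 2 SD = mean × (1 − 2 CV), which is negative once CV exceeds 0.5, whatever the distribution. It misleads only if someone reads it as a normal range. The protocol plans no such interval, says the data are not normal, and reports the observed minimum.

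**Which variables does the mechanism cover?** Only the hold times. VAS, FreNAQ and Tampa are bounded at both ends (0 to 10, 0 to 36, 17 to 68), and the push-up test counts repetitions in a fixed 30 seconds. A long open upper tail is not a sensible model for these.

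**Does the choice of summary reach the results?** Spearman's rho is computed from ranks. Taking logarithms of every positive hold time would change the mean and SD but leave every rank, and hence rho and its p value, as it was. The tabulated summary is not an input to the correlation, the significance level, the number of patients or the power.

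**The case for a change.** The strongest case for a change is this. The protocol does not leave the summary open; it fixes mean and SD for every quantitative variable and, in the same section, reports that the data are not normal. That is a flaw in what is written, not an item left to an analysis plan. Right skew is plausible for hold times without a stated cap, and resting pain is cut off below at 2 by the inclusion criteria. A reader given mean, SD and range cannot recover the median or quartiles. The investigators have already looked at histograms and skewness, so they know which variables are affected, and the remedy costs one sentence and a re-run of a table.

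Much of this stands. The mismatch is on the page, the log-normal arithmetic is correct, skewed hold times would be no surprise, and medians with quartiles would tell a reader something that the range does not.

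What does not stand is the step from there to misstated results. Non-normality does not establish right skew. The size of any distortion comes from assumed CVs. The mechanism does not extend to the questionnaires, the pain scale or the push-up count. Mean and SD are proper summaries of any distribution with finite variance, and they allow comparison with studies that report the same. Low cost alone does not make a change to the plan necessary when no result would move.

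**Conclusion.** No change to the plan is needed, because nothing in the study's results would gain from one. The description and the rank-based analysis follow different conventions, but the study's question is one of correlation. Every rho, every p value, the sample of 36 and the stated 86% power are the same under either summary. Mean, SD, minimum and maximum remain valid, and the reader is told that the data are not normal.

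The possible effect is confined to the descriptive table and to the hold-time tests: a mean 4% to 56% above the median if those times are log-normal with a CV of 0.3 to 1.2, and none if they are symmetric. The document does not show which applies. An analyst who finds marked skew can print the median and quartiles beside the planned columns. That is a matter of presentation and needs no revision of the protocol.

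### Does the correlation-strength scale need rewriting because it uses plain r, shares limits at 0.40 and 0.70, and calls its lowest band insignificant?

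*Protocol*

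**What the plan says.** The Statistical analysis section of the protocol bases all associations between endurance and pain, neck awareness and fear of movement on Spearman's rho, and then gives a verbal scale: "The strength of the relationships was assumed: $r > 0.90$ very strong; 0.70-0.90 strong; 0.40-0.70 moderate". The remaining bands are weak from 0.20 and, at the bottom, "0.40 weak, and $r < 0.20$ very weak/insignificant correlation". The sentence after the scale fixes the test criterion separately: "The statistical significance level (p) was accepted as 0.05". The sample size is in the Participants section: "The study included 36 patients who met the inclusion criteria".

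The protocol gives the scale no other role. No hypothesis, decision or sample-size statement depends on the labels.

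**The concern.** Four things in a short stretch of text look careless.

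- **Sign.** The bands are on r, not |r|. Longer endurance going with less pain or fear gives a negative coefficient, which is a natural result here. Taken literally, a rho of -0.60 is below 0.20 and would be graded very weak.
- **Shared limits.** 0.40 is both weak and moderate, and 0.70 is both moderate and strong. The limits 0.20 and 0.90 are assigned once, by the < and > signs.
- **A testing word in a size label.** The lowest band is called insignificant although significance has its own criterion. A reader might take 0.20 as the significance boundary.
- **Precision.** The weak band is 0.20 wide, while the sampling SD of rho near 0.30 with 36 patients is about 0.15. A label attached to a point estimate may not describe the underlying relationship.

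The description of each correlation is at stake. If adjectives were wrong or arbitrary, readers could carry away a stronger or weaker impression than the data support.

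**Working it through.** **Inputs.** n = 36 (Participants); Spearman's rho, the bands and the 0.05 level (Statistical analysis). Sidedness is not stated, so two-sided is assumed. The joint distribution is not given, so the simulations assume normal dependence without ties.

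**The protocol's own figure.** The Participants section reports post-hoc power that "was 86% with 36 individuals with cervical disc herniation", for the correlation of activity pain with deep flexor endurance. The coefficient behind it is not stated, so 86% cannot be reproduced. Solving backwards at n = 36 gives |r| of about 0.46 to 0.50 two-sided, or 0.42 to 0.45 one-sided. All of these are inside the moderate band and away from its limits. The figure does not use the scale.

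**Where significance falls.** With t = r·√(34/(1 − r²)) on 34 df:
- at |rho| = 0.20, t = 0.20 × √(34/0.96) = 1.19 and p = 0.242;
- the critical t is 2.032, so the critical |rho| = 2.032/√(34 + 2.032²) = 0.329.

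Every value in the lowest band is non-significant. The significance line lies inside the weak band, so values from 0.20 to 0.329 are weak and non-significant. The p-value shows this directly.

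**How often a shared limit matters.** For true rho from 0.20 to 0.39, the estimate rounds to 0.400 at three decimals in about 0.1% to 0.2% of samples and to 0.700 in about 0.02% or fewer. At two decimals, 0.40 appears in about 1% to 3%. The protocol describes ten endurance measures (counting right and left lateral flexors separately) and five outcomes (three pain ratings, neck awareness, kinesiophobia), hence 10 × 5 = 50 coefficients. If all had true values in that range, the expected number at 0.400 is 50 × 0.001 to 50 × 0.002, or 0.05 to 0.10. At two decimals it is 50 × 0.01 to 50 × 0.03, or 0.5 to 1.5, and the next decimal almost always settles the band.

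**How noisy the labels are at n = 36** (simulated, bands applied to |rho|):

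| True rho | very weak | weak | moderate | strong |
|---|---|---|---|---|
| 0.20 | 49% | 40% | 10% | 0% |
| 0.30 | 27% | 47% | 25% | 0% |
| 0.55 | 1% | 13% | 78% | 8% |

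A further simulation at a true rho of 0.80 gives strong in 85% of samples.

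Among samples with p < 0.05, the share at or above 0.40 is 49% at a true rho of 0.20, 51% at 0.22, 60% at 0.30 and 67% at 0.35. A significant weak relationship is therefore called moderate about as often as weak at the bottom of the band, and more often higher up.

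**What precision would take.** The 95% interval is tanh(atanh(r) ± 1.96·√((1 + r²/2)/(n − 3))). For r = 0.30 and n = 36: atanh(0.30) = 0.310, standard error √(1.045/33) = 0.178, interval −0.04 to 0.58. Keeping that interval within 0.20 to 0.40 needs roughly 340 to 360 patients.

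**Effect of rewording.** Absolute values and half-open limits are already what the simulation applies. The table is therefore the result after the edit: 47% at a true rho of 0.30 stays 47%.

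**The case for a change.** The strongest case for a change is that the defects are real, visible in the text and nearly free to repair. A written rule should not put a negative coefficient in the wrong band or assign one value twice, and adjectives are how many readers will remember the results. It is also true that a significant result in the weak band can only lie between 0.329 and 0.40, which pushes labels upward once attention is limited to p < 0.05.

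The textual points stand as a description of the sentence. They do not stand as a reason to alter the plan. The scale is introduced as one of strength, so nobody would grade -0.60 as very weak. In the lowest band the slash makes insignificant a synonym for negligible, and the arithmetic shows no conflict with the test. The upward push is real at 0.30 but close to even at 0.20, so it is not a general rule for weak relationships. It comes from combining a threshold on p with a small sample, and the wording of the scale neither causes nor cures it. A clause advising caution would change nothing that is computed or reported. A 95% confidence interval beside each rho would show the imprecision directly, but that is a reporting choice an analyst can make without amending the scale.

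**Conclusion.** No change to the plan is needed. The plain r, the shared limits and the stray word are clerical, and an analyst would resolve all three the same way: use |rho|, place a boundary value by a half-open rule, and take significance from the p-value alone. At n = 36 the lowest band contains no significant result (p = 0.24 at its upper edge, critical value 0.329), and exact boundary values are rare. No estimate, test or p-value depends on the scale.

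The label noise is genuine, with about 47% correct at a true rho of 0.30 against 78% at 0.55. It is a property of any cut-point applied to 36 patients, and rewording would not reduce it. These shares rest on normal dependence without ties. Integer questionnaire totals and repetition counts will produce some ties, so they are approximate. The conclusion does not depend on their exact values.
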